15. REFERENCES

16. APPENDIX A Performance Status Criteria

17. APPENDIX B Patient Zydelig Diary

18. APPENDIX C Inhibitors and Inducers of CYP3A

19. APPENDIX D Correlative Studies

- 19.1. Background and Overview
- 19.2. Time Points
- 19.3. Collection and Processing at Participating Sites for IHC and Immunologic Studies
- 19.4. Collection and Processing at Participating Sites for WES Studies
- 19.5. Sample Labeling
- 19.6. Shipping to VCU Massey Cancer Center
- 19.7. Shipping to Washington University
- 19.8. Sample Processing at VCU Massey Cancer Center
- 19.9. Sample Processing at Washington University
- 19.10. Sample Tracking
- 19.11. Pharmacokinetics Assessments
- 19.12. References

Tables

Table 1 Study Calendar

Table 2	Dose Modification Schedule
Table 3	Dose Modification for Toxicities Due to Zydelig
Table 4	Categorical Response Definitions
Table 5	Adverse Events – Treatment-Emergent Hematological & Non-Hematological Adverse Events in 5% of All Subjects
Table 6	Serious Adverse Events Reported as Possibly, Probably, or Definitely Related to Zydelig
Table 7	NCI Common Terminology for Adverse Events (CTCAE)
Table 8	Performance Status Criteria
Table 9	Sample Collection Table

Synopsis

Concept and Rationale:

Autologous stem cell transplantation (ASCT) represents a potential curative treatment for patients with relapsed and/or refractory (R/R) B-cell lymphomas, and is presently the modality that yields the best chance of prolonged progression-free survival in this population of patients.

Unfortunately, approximately half of these patients suffer from relapsed disease and die from their disease within 1 to 3 years after transplantation, depending on the disease status before transplantation.

Treatment of relapsed B-cell lymphomas after ASCT is challenging, and there are no standard of care or guidelines for this problem.

Rituximab maintenance may have some limited role in follicular lymphoma post autologous transplantation, but most of these patients have been exposed to rituximab and meet the criteria of being resistant to rituximab. With the increased number of patients who are undergoing transplantation and with the improved non-relapse mortality, relapse after transplant has become a larger factor in terms of survival. Relapses occur mostly within the first 2 years after ASCT.

Zydelig (Idelalisib) is the 1st marketed PI3K δ inhibitor that has been effective against indolent B-cell lymphomas (iNHL) with remarkable activity in heavily treated patients, leading to an overall response rate (ORR) of 57%, a median progression free survival (PFS) of 11 months and a median duration of response of 12.4 months.¹

We propose to incorporate Zydelig into a maintenance paradigm post ASCT for patients with iNHL and transformed iNHL (tiNHL). The goal of this strategy is to increase the likelihood that patients are able to maintain a remission after ASCT at 1 and 2 years of follow-up.

Mirroring the paradigm incorporating BCR/ABL TKI, lenalidomide and Sorafenib therapies in the post-transplant treatments of Ph+ ALL, MM, and FLT3 ITD AML respectively, we propose inhibiting the proliferation and survival of iNHL cells by blocking the B-cell receptor signaling (BCR) via inhibiting the downstream molecular target PI3K δ with Zydelig in the post-transplant setting.

[figure not shown]
Primary Objective(s):

1. Determine the toxicity and safety of incorporating Zydelig into the post- ASCT maintenance setting for iNHL and tiNHL immediately after ASCT.

Secondary Objective(s):

1. Assess the efficacy of incorporating Zydelig into the post-ASCT maintenance setting for iNHL and tiNHL immediately after ASCT with a corresponding endpoint of 1-year PFS after the transplantation.
2. 2-year Progression Free Survival (PFS).
3. Non-relapse mortality (NRM).
4. Overall survival (OS).
5. Correlatives studies:
 - a. To perform pharmacodynamics studies.
 - b. To understand mechanism of resistance to Zydelig.
 - c. To assess the effect of Zydelig on the immune system.

Study Design:

Number of Patients:

We will be studying a cohort of 34 patients with iNHL or tiNHL.

Main Criteria for Inclusion/Exclusion:

Inclusion Criteria - must meet all

1. iNHL as defined by follicular lymphoma (FL), marginal zone lymphoma (MZL), lymphoplasmacytic lymphoma/Waldenstrom disease (LPL/WM) and small lymphocytic lymphoma (SLL) or tiNHL as defined by large B cell transformation of any of the above entity.
2. Patients must be eligible to undergo high dose chemotherapy (HDT) followed by ASCT as a form of remission consolidation.
3. Patients without evidence of documented disease progression clinically or radiographically (stable disease [SD], partial remission [PR] or complete remission [CR]) who have had count recovery (ANC > 500 cells/mm³, non-transfused platelet count > 20,000 K/mm³) and are at least 30 days post ASCT, but no more than 120 days post ASCT.

Exclusion Criteria:

1. Lack of engraftment
2. Patients with active lymphoma CNS disease

3. Patients with active infection defined as requiring systemic antibiotic treatment and fever within 48 hours of screening.
4. Patients with progressive disease, as defined in protocol section 8.4
5. Patients who progressed while previously taking Zydelig
6. Patients with moderate to severe lung disease including:
 - 6.1. Patients requiring O2 supplementation
 - 6.2. Patients unable to walk 50 feet without stopping to rest
 - 6.3. Moderate to severe obstructive or restrictive disease of the lung
7. Patients with inflammatory bowel disease
8. Patients with active hepatic disease, liver cirrhosis, or known HBV/HCV infection
9. Patients with de novo diffuse large B-cell lymphoma
10. Patients with h/o PCP or CMV infections

Intervention and Mode of Delivery:

Oral Zydelig at 150 mg twice daily continuously on 28-day cycles.

Dose delays/modifications as below for Grade 2 or above for some hematological and non-hematological toxicities such hepatotoxicity, diarrhea/colitis/intestinal perforation, pneumonitis, infections, neutropenia and thrombocytopenia, or any other grade 3 non-hematologic toxicity considered at least possibly related to Zydelig.

Duration of Intervention and Evaluation:

iNHL and tiNHL patients will be eligible after ASCT.

Start of therapy would occur after engraftment, minimum at day 30 post ASCT and no later than 120 days post-ASCT.

Patients will continue on Zydelig up to one year or to progression/relapse/death or unacceptable toxicity, whichever occurs first.

HDT/ASCT will occur as soon as possible based on successful mobilization, collection and infusion of bone marrow or peripheral blood stem cells at a minimum of 2×10^6 CD34+/Kg of weight.

Myeloablative transplant preparative regimen is based on institutional standards.

Engraftment will be defined as ANC over 500 cells/mm³ and non-transfused platelet count of 20K/mm³. Standard supportive care in the post-transplant setting will be given.

Toxicities will be evaluated to include standard hematologic toxicities for solid tumors (i.e. count suppression etc.). Dose reductions will be pursued as described below for both hematologic and non-hematologic toxicities grade 2 and above

Initial dose will be 150 mg PO BID. Dose modifications for toxicities due to Zydelig will follow the package insert recommendations as below. For other severe or life-threatening toxicities related to Zydelig, withhold drug until toxicity is resolved. If resuming Zydelig after interruption for other severe or life-threatening toxicities, reduce the dose to 100 mg twice daily. Recurrence of other severe or life-threatening Zydelig-related toxicity upon rechallenge should result in permanent discontinuation of Zydelig. Toxicity, as well as graft failure will be monitored continuously throughout the trial.

Statistical Methods:

We are studying a cohort of 34 patients with iNHL or tiNHL. A single-stage open-label design will be used for the study. Please see section 14.0 Statistical Considerations for more information.

1. OBJECTIVES

1.1. Primary Objective

1.1.1. Determine the toxicity and safety of incorporating Zydelig into the post- ASCT maintenance setting for iNHL and tiNHL immediately after ASCT. Toxicity will be monitored continuously throughout the trial.

1.2. Secondary Objectives

1.2.1. Assess the efficacy of Zydelig into the post- ASCT maintenance setting for iNHL and tiNHL immediately after ASCT.

The corresponding endpoint is to report the 1-year PFS after the transplantation. PFS is defined as time to progression, relapse of the disease or death. The efficacy endpoint would be improvement of 1-year PFS after ASCT by 20% based on an approximate baseline PFS of 60% for iNHL and tiNHL.^{1,2} The expected 1-year PFS will be around 80%.

Survival without progression or death will be determined using the Kaplan-Meier estimates at 1 year post ASCT.

1.2.2. 2-year PFS.

2-year PFS will be determined using the Kaplan-Meier estimates at 2 years post ASCT.

1.2.3. Non-relapse mortality (NRM).

NRM is defined as death in the absence of competing risks, relapse or progression of disease. This secondary endpoint will be characterized and presented as a cumulative incidence at 3 months and 12 months after SCT.

1.2.4. Overall survival (OS).

Survival without death will be determined and presented as Kaplan-Meier estimates at 1 and 2 years post ASCT.

1.2.5. Correlative studies.

See Appendix D.

2. BACKGROUND

2.1. Zydelig (Zydelig, GS-1101, Cal-101)

Zydelig is an inhibitor of PI3Kinase delta which is highly expressed in malignant lymphoid B-cells. PI3K δ inhibition results in apoptosis of malignant tumor cells. In addition, Zydelig inhibits several signaling pathways, including the B-cell receptor. Zydelig was recently approved by the U.S. Food and Drug Association (FDA) for the treatment of the following:

- relapsed chronic lymphocytic leukemia (CLL), in combination with rituximab, in patients for whom rituximab alone would be considered appropriate therapy due to other co-morbidities
- relapsed follicular B-cell non-Hodgkin lymphoma (FL) in patients who have received at least two prior systemic therapies
- relapsed small lymphocytic lymphoma (SLL) in patients who have received at least two prior systemic therapies.^{1,2, 3-5}

2.2. Study Disease – Indolent B-cell Lymphomas/Transformed B-cell Lymphomas

Early published clinical trial of Zydelig in multiple relapsed and treated indolent B-cell lymphomas showed a respectable ORR of 57% (6% CR) a short median time to response of 1.9

months and a prolonged median duration of response of 12.5 months. Responses were seen in all lymphoma subtypes. The estimated median progression-free survival and overall survival were 11 months, and 20 months, respectively. The estimated survival rate at one year was 80%. This population of patients included patients who already had undergone HDT/ASCT, and these patients had no different responses to Zydelig compared to the other patients.⁴

There are some reports in the literature showing that the PI3K/Akt/mTOR signaling pathway might be activated in aggressive B-cell lymphoma.⁶⁻¹⁰ Other PI3K inhibitors, such as SAR245408, showed some activity in 25% of aggressive B-cell lymphoma.¹¹

2.3. Rationale

Autologous stem cell transplantation (ASCT) represents a potential curative treatment for patients with relapsed and/or refractory (R/R) B-cell lymphomas and is presently the modality that yields the best chance of prolonged survival without disease in this population of patients. Unfortunately, approximately half of these patients suffer from relapsed disease and die from their disease in 1 to 3 years after transplantation depending, on the disease status before transplantation.

Treatment of relapsed B-cell lymphomas after ASCT is challenging, and there are no standard of care or guidelines for this problem.

Rituximab maintenance may have some limited role in follicular lymphoma post autologous transplantation, but most of these patients have been exposed to rituximab and meet the criteria of being resistant to rituximab. With the increased number of patients who are undergoing transplantation and with the improved non-relapse mortality, relapse after transplant has become a larger factor in terms of survival. Relapses occur mostly within the first 2 years after ASCT.

Zydelig is the 1st marketed PI3K δ inhibitor that has been effective against indolent B-cell lymphomas (iNHL) with remarkable activity in heavily treated patients, leading to response rate (ORR) of 57%, a median progression free survival (PFS) of 11 months and a median duration of response of 12.4 months.⁴

We propose to incorporate Zydelig into a maintenance paradigm post ASCT for patients with iNHL and transformed iNHL (tiNHL). The goal of this strategy is to increase the likelihood patients are able to maintain a remission after ASCT at 1 and 2 years of follow-up.

Mirroring the paradigm incorporating BCR/ABL TKI and Sorafenib targeted therapies in the post-transplant treatments of Ph+ ALL and FLT3 ITD AML respectively, we propose inhibiting the proliferation and survival of iNHL cells by blocking the B-cell receptor signaling (BCR) via inhibiting the downstream molecular target PI3K δ with Zydelig in the post-transplant setting.

2.4. Correlative Studies Background

Please refer to Appendix D

3. PATIENT SELECTION

3.1. Eligibility Criteria

3.1.1. Inclusion Criteria (must meet all)

1. Histologically documented (by HPI or pathology report) iNHL as defined by follicular lymphoma (FL), marginal zone lymphoma (MZL), lymphoplasmacytic lymphoma/Waldenstrom disease (LPL/WM) and small lymphocytic lymphoma (SLL) or tiNHL as defined by large B cell transformation of any of the above entities including chronic lymphocytic leukemia (CLL)
2. Patients must be eligible to undergo high dose chemotherapy (HDT) followed by ASCT as a form of remission consolidation
3. Patients without evidence of documented disease progression clinically or radiographically after ASCT (stable disease (SD), partial remission (PR) or complete remission (CR)) who have had count recovery (ANC > 500 cells/mm³, non-transfused platelet count > 20,000 K/mm³) and are at least 30 days post ASCT but no more than 120 days post ASCT

3.1.2. Prior Therapy

Patients may have received any prior therapy deemed necessary for them to be eligible to HDT/ASCT except for patients whom have progressed while on Zydelig. Patients who have responded to Zydelig previously are eligible for enrollment on the protocol.

3.1.3. Age >18

3.1.4. ECOG performance status <4 (see Appendix A).

3.1.5. Life expectancy of greater than four months.

3.1.6. Patients must have normal organ function as defined below (after the HDT/ASCT):

- total bilirubin \leq 2x institutional upper limit of normal
- AST(SGOT)/ALT(SGPT) <2.5 X institutional upper limit of normal
- Creatinine \leq 1.5x institutional upper limit of normal OR creatinine clearance \geq 60 mL/min/1.73 m² for patients with creatinine levels \geq 1.5x upper limit of normal.

3.1.7. Because the effects of Zydelig on the developing human fetus are unknown, women of child-bearing potential and men must agree to use adequate contraception (hormonal or barrier method of birth control; abstinence) prior to study entry and for the duration of study participation. Female subjects of childbearing potential should have a negative pregnancy test within 72 hours prior to receiving the first dose of Zydelig. Male subjects must agree to use an adequate method of contraception starting with the first dose of the study drug Zydelig. Female and male participants must agree to use contraception for at least 30 days after the last dose of Zydelig. Women of childbearing potential is defined as women who continues to have menstrual periods, have not had a tubal ligation, or the removal of fallopian tubes, ovaries or uterus.

3.1.8. Ability to understand English and the willingness to sign a written informed consent document.

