3.2. Exclusion Criteria

- 3.2.1 Patients who have had chemotherapy or radiotherapy within 2 weeks of first dose of Zydelig.
- 3.2.2 Patients receiving any other investigational agents within 30 days of receiving Zydelig
- 3.2.3 Patients who were previously exposed to Zydelig and experienced progression of disease.
- 3.2.4 History of allergic reactions attributed to compounds of similar chemical or biologic composition to Zydelig.
- 3.2.5 Patients with active and/or untreated CNS lymphoma will not be eligible.
- 3.2.6 Patients with inflammatory bowel disease.
- 3.2.7 Uncontrolled intercurrent illness including, but not limited to ongoing or active infection (defined as requiring systemic antibiotic treatment and fever within 48 hours of screening), symptomatic congestive heart failure (patients with NYHA score of III and above are excluded), unstable angina pectoris, cardiac arrhythmia, or psychiatric illness/social situations that would limit compliance with study requirements.
- 3.2.8 Women who are pregnant or nursing or plan to become pregnant or nurse during the course of the study.
- 3.2.9 Positive HIV status.
- 3.2.10 Patients with lack of count recovery as defined by ANC > 500 cells/mm³, non-transfused platelet count > 20,000 K/mm³.
- 3.2.11 Patients who are unable to swallow pills.
- 3.2.12 Patients with moderate to severe lung disease including:
 - Patients requiring O₂ supplementation
 - Patients unable to walk 50 feet without stopping to rest
 - Obstructive lung disease as defined by pre-transplant FEV₁ ≤ 60% of predicted.
 - Restrictive lung disease as defined by pre-transplant FVC < 60% of predicted.
- 3.2.13 Patients taking strong CYP3A4 inhibitors or inducers with Risk X (Avoid Combination) according to Lexicomp. Please see appendix C for more information.
- 3.2.14 Patients with active hepatic disease, liver cirrhosis, or known HBV/HCV infection.
- 3.2.15 Patients with de novo diffuse large B-cell lymphoma.

3.2.16 Patients with h/o PCP pneumonia or positive CMV viremia confirmed twice at least 1 day apart at screening.

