6. REQUIRED DATA/STUDY CALENDAR

Pre-Study Testing Intervals

To be completed within 16 DAYS before study treatment:

- All blood work
- History and physical

To be completed within 28 DAYS before study treatment:

- Any X-ray, scan of any type (e.g., CT or MRI) or ultrasound that is utilized for tumor measurement

To be completed within 42 DAYS before study treatment:

- Any X-ray, scan of any type (e.g., CT or MRI) or ultrasound that is not utilized for tumor measurement
- Bone marrow biopsy and aspirate (unilateral) is required if there washistory of bone marrow involvement.

	Prior to Treatment	Cycle 1 Day 1	Cycle 1 Day 8 ± 3 days	Cycle 1 Day 15 ± 3 days	Day 1 of Each Subsequent Cycle ± 3 days ^l	Cycle 2 Day 15 ± 3 days	Cycle 3 Day 15 ± 3 days	End of Treatment* * ± 3 days	Time of Restaging and Post-treatment Follow-up*, %
Tests & Observations									
History & Progress Note	X	X			X			X	X
Physical Examination	X	X			X			X	X ^j
Pulse, Blood Pressure	X	X			X			X	X
Height	X								
Weight	X	X			X			X	X
Performance Status	X	X			X			X	X
Drug Toxicity Assessment	X	X			X			X	
Solicited Abnormalities/AEs	X	X ^A			X ^A			X	
Laboratory Studies									
CBC, Diff, Platelets	X	X			X			X	X
Serum Creatinine, CrCl (est), BUN	X	X			X			X	X
Serum Electrolytes	X	X			X			X	X
AST, ALT, Alk Phos, Bilirubin	X	X		X	X ^A	X	X	X	X
Uric Acid, Phosphate, LDH	X	X			X			X	X
Blood CMV PCR	X	X			X			X	
Beta2-Microglobulin	X							X	

Serum or Urine BHCg	X ^B							X	
Thyroid Function Tests (T3,T4, TSH)	X ^E				X ^E			X	
Triglycerides	X ^I							X	
HIV~	X ^{C~}							X	
HBsAg~, Anti-HBc~Ab,HepC Ab~	X~							X	
ECG	X		X ^F					X	
Staging									
CT/MRI (chest/abd/pelvis) with Tumor Measurements	X							X	X ^D
CT Neck	X							X	X ^D
PET (or PET/CT)	X							X	X ^D
Bone Marrow Asp & Biopsy	X							X ^G	X ^G
Histologic Review	X							X ^K	
Correlative Samples	X ^H	X ^H						X ^H	X ^H

Table 1

* Restage every 3 cycles during treatment (i.e., cycles 3, 6, 9, 12, etc.), then every 3 months for 1 year, then every 6 months for another year.

** If off study prior to month 12 study treatment

% Starting at cycle 15 through cycle 24: Visit window +/- 4 weeks. Starting at cycle 27 through cycle 36: Visit window +/- 12 weeks.

^ Monitor ALT, AST, Alk Phos and bilirubin in all patients every 2 weeks (or 15 days) for the first 3 cycles of treatment, than every 4 weeks during subsequent cycles.

~ If done before the transplant, no need to repeat them.

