A. Abnormalities/adverse events should be solicited, and severity graded, on day 1 of each cycle of treatment.

B. In women of childbearing potential (as defined in Section 3.1.7). A negative serum or urine HCG test is required within 14 days prior to study.

C. Patients with known HIV positivity are excluded.

D. CT, PET or PET/CT done PRN to follow measurable disease. Scan to be done with or without PET depending on the patient disease status.

- E. Thyroid function tests every 3 cycles while on treatment and at completion of protocol therapy(Prior to treatment, C3D1, C6D1, C9D1, C12D1).
- F. ECG on day 8 of cycle 1, and then as clinically indicated. The steady-state (day 8) ECG is a requirement of the FDA under the Alliance IND for Zydelig.
- G. Repeat bone marrow aspirate and biopsy to confirm CR only if involved at baseline. Also a bone marrow aspirate/biopsy will be done if suspicion of bone marrow involvement.
- H. See protocol 19.2 Time Points of appendix D Correlative Studies
- I. Triglycerides Day 1 of cycles 3, 6, 9, 12 and then every 3 months until month 24. Then again at months 24, 30, & 36.
- J. Physical Exam during follow-up.
- K. Only if there is progression, as judged by the Investigator

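### The study calendar accepts a pregnancy test up to 14 days old where Section 3.1.7 asks for 72 hours, and the definition of childbearing potential, read literally, exempts women whose periods have stopped

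*Combined protocol and SAP*

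**What the plan says.** Two places in the protocol set the timing of the pre-treatment pregnancy test.

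- Section 3.1.7 (eligibility): "Female subjects of childbearing potential should have a negative pregnancy test within 72 hours prior to receiving the first dose of Zydelig".
- Section 6, Table 1, footnote B: "A negative serum or urine HCG test is required within 14 days prior to study". The footnote limits this to a defined group: "In women of childbearing potential (as defined in Section 3.1.7)".

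The Table 1 row for the test is marked at the pre-treatment column and at end of treatment. Cycle 1 Day 1 has no mark. Section 6 also gives a general interval for all blood work: "To be completed within 16 DAYS before study treatment".

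The definition is in Section 3.1.7: "Women of childbearing potential is defined as women who continues to have menstrual periods". It then adds that the woman has had no tubal ligation and no removal of the tubes, ovaries or uterus. It contains no age limit, no minimum time without periods and no menopause criterion. The same section attaches its pre-treatment and on-treatment contraception duty to that group: "women of child-bearing potential and men must agree to use adequate contraception".

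**The concern.** The test is the check that keeps a pregnant woman from starting the drug. Section 10.5 warns of fetal harm on the basis of animal findings and reports teratogenicity in rats at 12 times the exposure of patients on 150 mg twice daily. Two features of the text weaken the check.

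First, the two rules differ in length, in force (*should* against *required*) and in the event they count back from (first dose against study). The stricter interval carries the softer verb. Someone scheduling visits from the calendar would see only the looser rule.

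Second, a definition that depends on current menstruation can be defeated by the condition the test is meant to find. An unrecognized pregnancy stops periods and so, on the literal wording, takes the woman out of the group to be tested. It also takes her out of the contraception duty before and during treatment.

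**Working it through.** No power, error-rate or event figure enters this point. The check compares the texts and converts the two windows to one unit.

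**Window**

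| | Section 3.1.7 | Table 1, footnote B |
|---|---|---|
| Maximum age of test | 72 h = 3 days | 14 days = 14 × 24 = 336 h |
| Verb | should | required |
| Counted back from | first dose | study |

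Difference: 14 − 3 = 11 days (336 − 72 = 264 h). Ratio: 336 / 72 = 4.67.

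The 11 days assume that the footnote's reference to the study means the first dose. The general intervals in Section 6 count back from study treatment, which supports that reading. If it means study entry instead, the test could be more than 14 days old at first dose. The 16-day limit on blood work would then still bound a serum test, but it does not mention urine tests, which footnote B also accepts.

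A test done 4 to 14 days before dosing therefore satisfies footnote B and misses Section 3.1.7. A test done within 72 hours of the first dose satisfies both, so the rules can be met together. The protocol does not make a site do so in binding terms.

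**Definition**

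The sentence in Section 3.1.7 is poorly constructed. Its natural reading is that a woman must still be menstruating and must not have had sterilizing surgery. Apply that to a woman with intact organs whose periods have stopped:

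1. She is not of childbearing potential under Section 3.1.7, so its 72-hour test does not apply.
2. Footnote B uses the same definition, so its 14-day test does not apply.
3. The contraception duty before and during treatment does not apply.

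The remaining safeguards are:

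- Section 3.2.8 excludes "Women who are pregnant or nursing or plan to become pregnant or nurse during the course of the study", but orders no test.
- Section 3.1.7 covers everyone after treatment: "Female and male participants must agree to use contraception for at least 30 days after the last dose of Zydelig". This duty begins after exposure has ended.
- Section 10.5 advises against becoming pregnant on treatment, but orders no test.
- Section 4 has the coordinating center check eligibility documents, but against the same definition.
- The end-of-treatment test comes after exposure.

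None of these requires a test in this woman before her first dose.

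**The case against.** The strongest reply is that the rules do not truly conflict. Section 3.1.7 is an eligibility criterion, nothing says the calendar overrides it, and a site dosing on a 10-day-old test has not followed it. The protocol uses *should* for many instructions that are plainly meant to be followed, such as restaging every 3 cycles, so the verb may be only a drafting habit. The two texts could also describe two tests, one at screening and one just before dosing. On the definition, continuing to have periods is everyday language for not yet menopausal. On that reading, a woman who has missed a period is still tested.

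Part of this stands. A careful site can comply with both rules, the eligibility review in Section 4 may catch an old test, and the premenopausal reading is possible. But the two-test reading does not fit Table 1, which marks one test before treatment and none at Cycle 1 Day 1. A coordinating center would find it hard to refuse a test that meets the rule worded as required by pointing to one worded as should. The definition does not state the premenopausal meaning, and a safety criterion should not depend on a generous reading.

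**Conclusion.** The concern holds, and the text is wrong as written. Under footnote B the test may be 14 days old at first dose against 3 days under Section 3.1.7, a gap of 11 days if the footnote counts back from the first dose. Under the literal definition, a woman with intact organs whose periods have stopped is not required to have a test at all. The second conclusion depends on reading the sentence as requiring continuing menses.

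The 11 days measure a difference in the rules, not a probability of harm. The documents do not say how many of the 34 patients would be women in either position. There is no effect on the primary endpoint, the sample size or any analysis. The change should be made because the safety benefit is clear and the cost is slight.

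**What to change.** - Reword footnote B so that the negative test falls within 72 hours before the first dose of Zydelig, matching Section 3.1.7 in both length and anchor.
- In Section 3.1.7, replace *should* with *must*.
- Define childbearing potential as any woman who is neither surgically sterile nor of established postmenopausal status, whatever her current menses. One workable criterion is menopause established before chemotherapy. The exact criterion is a clinical choice that the documents do not settle.
- Optionally, add a mark for the test at Cycle 1 Day 1 in Table 1.

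The cost is a wording amendment to Section 3.1.7 and footnote B, plus a few additional blood or urine tests.
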